10.2.4.3. Renal Impairment

Renal impairment is defined as events included in the following broad SMQs: acute renal failure, chronic kidney disease, proteinuria, renovascular disorders, or tubulointerstitial diseases.

Summaries will include a summary of the crude incidence of myalgia TEAEs and SAEs by system organ class and preferred terms.

10.3. Clinical Laboratory Evaluations

Laboratory parameters will be summarized in both conventional and standard international system of units using descriptive statistics at Baseline and at each on-study evaluation. Baseline is defined as the mean of all available evaluations prior to the first administration of investigational product.

The normal ranges of the selected lab parameters are defined below. The abnormal indicators of the selected lab parameters will be derived based on these normal ranges (inclusively):

- ALP 44-122 U/L
- ALT 0-45 U/L
- AST 0-45 IU/L
- GGT 0-65 IU/L (male) 0-60 IU/L (female)
- Total Bilirubin 1.71-12.3 umol/L
- Direct Bilirubin 0-0.4 mg/dL
- Cholesterol 0-169 mg/dL (age ≤19), 0-199 mg/dL (age >19)
- LDL 0-109 mg/dL (age ≤19), 0-99 mg/dL (age >19)
- HDL >39 mg/dL
- Creatinine 0.57-1.27 mg/dL
- Creatine 0.0-0.7 mg/dL (male) 0.1-1.0 mg/dL (female)
- CK 41-439 U/L (male, age 18-50 years old), 41-331 U/L (male, age 51-80 years old),

32-182 (female, age 18-80 years old)

For the other lab parameters, the normal ranges and abnormal indicators are based on the values in the data from the central or local labs.

In addition, shift tables (i.e., low-normal-high at Baseline versus low-normal-high at post-Baseline visit in a 3-by-3 contingency table) from Baseline to worst value, last value, and at each scheduled post Baseline visit will be provided for hematology and serum chemistry to assess changes in laboratory values from Baseline to each on-study evaluation from the central or local labs. The subjects meeting Hy's law criteria (defined as AST or ALT ≥ 3 xULN together with total bilirubin ≥ 2 xULN at any timepoint) will be summarized by visit.

Urine chemistry and urinalysis results will not be summarized but will be provided in a data listing.

All clinical laboratory data (including central and local) will be presented in by-subject data listings.

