8.4. Subject Withdrawal Criteria

Subjects who are discontinued from investigational product should be requested to continue with study visits until Month 60/EOS. Subjects who discontinue investigational product may be requested to come in for an Unscheduled Visit at the discretion of the Investigator depending on the timing of their next scheduled study visit.

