15.3.2. Clinical Laboratory Evaluations

Laboratory parameters and vital signs will be summarized using descriptive statistics at baseline (defined as the last assessment performed before the first dose of investigational product in Study 977-311) and at each scheduled postbaseline visit. The change from baseline will also be summarized. ECGs will be summarized using frequency at each visit. The shift from baseline will also be summarized. Baseline is defined as the mean of all available evaluations before treatment (except for lipoprotein assessments where Baseline will be Day 1).

In addition, shift tables from baseline based on normal ranges will be provided for hematology, coagulation, and serum chemistry to assess changes in laboratory values from baseline (Day 1) to each evaluation through Month 60 (EOS) or ET.

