10.2.1. Treatment-emergent Adverse Events

An AE is defined as a treatment-emergent adverse event (TEAE) in the DB period if it meets one or more of the following criteria:

- An AE starting on or after the first study drug dose.
- An AE occurring prior to the first study drug dose that worsens (increase in grade) after the first study drug dose during Double-Blind period.
- An AE with a missing start date but with an end date after the first study drug dose date.
- Any AE started later than the 30 days of the last dose of study drug is not counted as a TEAE.

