10.4. Vital Signs

The results and change from Baseline to each on-study evaluation visit will be summarized for weight, oral temperature, sitting heart rate, respiratory rate and sitting blood pressure.

All vital sign data will be presented in by-subject data listings.

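### Laboratory, Hy's law and vital-sign tables have no last-dose limit while AE summaries stop at 30 days after last dose, so on-drug and off-drug values are pooled as FDC safety

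*SAP*

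**What the plan says.** The safety tables run on two different windows.

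**Laboratory values and vital signs: no last-dose limit**
- SAP 10.3, by-visit summaries: "Laboratory parameters will be summarized in both conventional and standard international system of units using descriptive statistics at Baseline and at each on-study evaluation".
- SAP 10.3, shift tables: "from Baseline to worst value, last value, and at each scheduled post Baseline visit will be provided for hematology and serum chemistry".
- SAP 10.3, Hy's law: an aminotransferase criterion "together with total bilirubin ≥ 2 xULN at any timepoint) will be summarized by visit".
- SAP 10.4: "The results and change from Baseline to each on-study evaluation visit will be summarized for weight", and likewise for the other vital signs.
- Protocol 15.3.2 takes shift tables "to each evaluation through Month 60 (EOS) or ET".
- SAP 5.5 admits only scheduled visits to the analyses; unscheduled visits are listed.

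**Adverse events: limited to 30 days after last dose**
- SAP 10.2.1: "Any AE started later than the 30 days of the last dose of study drug is not counted as a TEAE".
- SAP 10.2.3 restricts every AE summary to TEAEs.

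**Who is in the tables**
- SAP 4.1 and 10: everyone with at least one FDC dose, so a subject remains in the safety population after stopping.
- Protocol 8.4: "Subjects who are discontinued from investigational product should be requested to continue with study visits until Month 60/EOS". Protocol 7.6 and 9.7.3 say the same.

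For efficacy and exploratory endpoints, SAP 9.1 and 9.2 state openly that data after discontinuation are included. No safety section has a matching statement.

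**The concern.** The primary objective is the long-term safety of the FDC tablet, and there is no comparator arm. Nothing in the planned laboratory and vital-sign tables lets a reader separate what happens on the tablet from what happens after it is withdrawn.

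The off-drug subjects are also a selected group. The protocol makes stopping mandatory for the hepatic criteria of Table 5 (8.4.1), for related AEs of Grade 3 or above (8.4.1.1), and after a drug holiday of more than 30 days (14.1.3.1). It then asks these subjects to go on attending. Late-visit values will come disproportionately from people who had a safety problem.

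Two consequences follow. A change that reflects loss of drug effect can enter the worst-value or last-value shift as laboratory worsening in an FDC safety table. And the same late liver event can be treated differently in two tables that a reader would expect to agree.

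**Working it through.** The plan states no figure on this point to reproduce. The check compares the rules and then sizes the overlap.

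**1. One subject, two tables.** Suppose a subject takes the last dose at Month 6, stays in the study, and at the scheduled Month 12 visit meets the Hy's law criteria, with the liver AE starting at that time.
- Hy's law table (SAP 10.3): counted, because any scheduled timepoint qualifies.
- Worst-value shift (SAP 10.3): counted.
- Hepatic-injury TEAE summary (SAP 10.2.4): not counted, because onset is about six months after last dose.
- AE listing (SAP 10.2.3): shown.

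**2. Scheduled visits off drug.** Protocol Table 3 gives 12 scheduled post-baseline laboratory visits: Months 1, 3, 6, 12, 18, 24, 30, 36, 42, 48, 54 and 60. For a subject who stops and stays to Month 60, the visits more than 30 days after last dose are:

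| Stops at | Visits off drug | Longest time off drug |
|---|---|---|
| Month 6 | 9 of 12 | 54 months |
| Month 12 | 8 of 12 | 48 months |
| Month 24 | 6 of 12 | 36 months |
| Month 36 | 4 of 12 | 24 months |
| Month 48 | 2 of 12 | 12 months |

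For the Month 6 stopper, AEs starting in about 54 − 1 = 53 of those months are outside every AE summary, while the laboratory values from the same months are in.

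**3. Share of Month 60 values off drug.** The documents give neither a stopping rate nor the proportion of stoppers who stay. Assume a constant yearly stopping rate a, a proportion r of stoppers retained, no other loss, and N = 133 (Protocol 7.2). Thirty days is 30/(365.25/12) = 0.986 months.

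- Off drug for more than 30 days by Month 60: p = 1 − (1 − a)^((60 − 0.986)/12) = 1 − (1 − a)^4.918
- Share of Month 60 values: r·p / (1 − p + r·p)

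Example, a = 10%: p = 1 − 0.90^4.918 = 0.404. With r = 1 the share is 40.4%. With r = 0.5 it is 0.202/(0.596 + 0.202) = 25.3%.

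| a per year | Off drug at Month 60, all stay (of 133) | Share of Month 60 values, all stay | Share, half stay | Share of all scheduled post-baseline values, all stay |
|---|---|---|---|---|
| 3% | 18.5 | 13.9% | 7.5% | 6.5% |
| 5% | 29.7 | 22.3% | 12.5% | 10.5% |
| 10% | 53.8 | 40.4% | 25.3% | 19.8% |
| 15% | 73.2 | 55.0% | 38.0% | 28.1% |

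**4. Illustration for ALP.** Protocol 5.4.3 reports, for OCA 5 mg + BZF 400 mg IR in Study 747-214, an LS mean fall of 183.1 U/L (61.4%). That implies a starting level of about 183.1/0.614 = 298 U/L and a treated level of about 298 − 183 = 115 U/L. The SAP 10.3 upper limit is 122 U/L. A subject entering at about 115 who stopped and returned fully to about 298 would be tabulated as a normal-to-high shift. This is back-calculated from a group mean and assumes full rebound, which no section reports. It shows the mechanism only.

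**The case against.** The strongest reply is that off-drug data are kept on purpose. Protocol 8.4.1.1 asks stoppers to continue so that safety data are collected, 14.1.9 warns that drug-induced liver injury may appear or progress after the drug is stopped, and 15.3.2 requires shift tables through Month 60 or ET. An on-treatment-only display would push late liver cases out of the main tables. This stands: the defect is the lack of separation, and the remedy must add tables without replacing any.

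There are partial safeguards. Listings mark post-treatment days with a P (SAP 5), potential hepatic and renal injury is adjudicated case by case (Protocol 14.3), and Hy's law is shown by visit. The study is descriptive, with no hypothesis. These soften the point, but none puts on-drug and off-drug values in separate summaries.

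Some stronger readings are tempting and are not supported:
- *Every on-study value enters the tables.* SAP 5.5 limits the analyses to scheduled visits.
- *AEs are no longer captured after 30 days.* Protocol 14.1.4.1 continues collection until participation ends, and SAP 10.2.3 lists all AEs. Only the summaries stop.
- *If a share d of subjects is off drug, a reversible effect is understated by d.* That arithmetic needs an untreated baseline. Subjects must be actively taking parent-study drug to enrol (Protocol 8.2), so for someone already on the combination, change from baseline may be small on drug and move away from zero after stopping. The ALP illustration runs in that opposite direction. No single dilution percentage can be given.

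**Conclusion.** The point holds as a gap in the stated rules. Followed as written, the SAP pools on-drug and off-drug values from scheduled visits in the laboratory, shift, Hy's law and vital-sign tables, and it applies a different window to AE summaries. A late liver event can therefore appear under Hy's law and be absent from the hepatic-injury TEAEs.

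Confidence is high for the text and lower for the size. The Month 60 share of about 14% to 55% (all stoppers stay) or about 7.5% to 38% (half stay) rests on an assumed 3% to 15% yearly stopping rate. Stoppers are only requested to continue, so retention could be lower still. The direction of any bias in a given parameter cannot be stated in advance, and no specific harm has been shown for vital signs beyond the same pooling. It should be corrected because it touches the primary objective, but it does not undermine the study.

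**What to change.** 1. **Reconcile the TEAE window first.** The SAP's 30-day limit is absent from the TEAE definition in Protocol 14.1.1.3, although SAP 11 reports no deviations from the protocol. Settle one rule and record it in both documents.
2. **Add an on-treatment flag in SAP 10.3 and 10.4:** from the first FDC dose in Study 977-311 through the last dose plus the same number of days as the reconciled TEAE window.
3. **Present two versions side by side,** on-treatment and all on-study, for by-visit laboratory summaries, worst-value and last-value shifts, Hy's law and vital signs. The all-on-study version keeps what Protocol 15.3.2 requires.
4. **Classify each Hy's law case by time since last dose,** so that no late case is dropped and each can be matched to the AE tables.

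The cost is SAP wording, one derived variable and additional tables. The last-dose date is already needed for study-day numbering, exposure and TEAEs (SAP 5, 10.1, 10.2.1). The on-treatment columns will have smaller numbers at late visits: a Month 6 stopper would leave 9 of 12 visits from them.

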5. INTRODUCTION

5.1. Overview of Primary Biliary Cholangitis, Obeticholic Acid, and Bezafibrate

Primary biliary cholangitis (PBC) is a rare, autoimmune, cholestatic liver disease, predominantly affecting women over 40 years of age (EASL 2017, Lindor 2019). It is estimated that the prevalence of PBC is 1 in 1000 women over the age of 40 years with up to 100,000 patients diagnosed with PBC in the United States (US) (Lu 2018); less than 10% of patients with PBC are male (EASL 2017). The natural history of the disease is well understood and characterized by progressive destruction of intrahepatic bile ducts resulting in chronic cholestasis, portal inflammation, and fibrosis that can lead to cirrhosis and ultimately liver failure (Murillo Perez 2020, Selmi 2011).

The most common presenting symptoms of PBC are pruritus and fatigue. The diagnosis of PBC can be met with at least 2 of the following criteria: 1) biochemical evidence of cholestasis with elevation of serum ALP; 2) presence of anti-mitochondrial autoantibodies, or other PBC-specific autoantibodies; or 3) histological evidence of nonsuppurative destructive cholangitis and destruction of interlobular bile ducts (Lindor 2019).

The treatment goal for patients with PBC is to improve transplant-free survival. Historically, ALP and bilirubin levels have been the primary biochemical markers used by clinicians to determine the risk of progression and to evaluate response to treatment (Kowdley 2022, Murillo Perez 2020, Corpechot 2011, Lammers 2014). Recent data suggest that optimal survival benefit is realized when normalization of either ALP ($<ULN$) or total bilirubin ($<0.6 \times ULN$) are achieved (Murillo Perez 2020, Soret 2021). High GGT levels have also been associated with increased risk of mortality and liver transplant, supporting the role of GGT as an additional prognostic biomarker of PBC (Gerussi 2021). AST and ALT may also provide additional prognostic information as the AST/ALT ratio is associated with disease progression, particularly in patients with advanced histologic stages III to IV (Gatselis 2020). The relative importance of each of these plasma biomarkers remains a key focus of clinical research. It is also increasingly clear that the amount of time an individual spends with abnormal biochemistries is predictive of increased risk (Kowdley 2023, Soret 2021).

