- Unscheduled visits as needed in the event of signs or symptoms of potential hepatic and/or muscular injury or decompensation or if laboratory alerts have been triggered

It is important that the laboratory assessments be completed as required and that the central laboratory be used for assessments whenever possible. In the event that a subject cannot return to the clinic for a scheduled or unscheduled visit, or there is an event that triggers a need for an immediate assessment, the use of a local lab is permissible at the discretion of the Investigator. In these cases, the Investigator will obtain the laboratory results and the laboratory normal ranges.

The process for assessing criteria is presented in Figure 2, and the specific threshold(s) for each laboratory analyte to trigger investigational product interruption are summarized in Table 5.

Figure 2: Management Algorithm for Potential Hepatic and/or Muscular Injury

CK=creatine kinase; INR=international normalized ratio; IP=Investigational Product; PK=pharmacokinetic

Notes: Laboratory assessments include: ALT, ALP, AST, GGT, direct and total bilirubin, INR, and CK.

PK sampling should be conducted within 7 days of IP interruption; close monitoring including physical exams and repeat biochemistry labs should occur as often as deemed appropriate by the Investigator (Table 4).

Table 4: Laboratory Criteria for Monitoring of Potential Hepatic and Muscular Injury for Interruption^a of Investigational Product

Baseline ^b	Treatment Emergent	Liver Signs and Symptoms ^c
Any value	Any hepatic enzyme elevation (TB, ALP, AST, ALT, GGT)	Yes
ALT or AST Normal	ALT or AST ≥ 3 x ULN and TB ≥ 2 x BL	Yes or No
	ALT or AST ≥ 3 x ULN and INR >1.5	Yes or No
	ALT or AST ≥ 5 x ULN and Any TB	Yes or No
ALT or AST Elevated	ALT or AST ≥ 2 x BL and TB ≥ 2 x BL	Yes or No
	ALT or AST ≥ 2 x BL and INR >1.5	Yes or No
	ALT or AST ≥ 3 x BL (or ≥ 300 U/L, whichever occurs first) and Any TB	Yes or No
TB \leq ULN	TB ≥ 2 x BL and $>$ ULN	Yes or No
TB $>$ ULN	TB ≥ 1.5 x BL or ≥ 3.0 mg/dL, whichever occurs first	Yes or No
ALP \leq ULN	ALP ≥ 2 x BL and $>$ ULN	Yes or No
ALP $>$ ULN	ALP ≥ 2 x BL or ≥ 1000 U/L, whichever occurs first	Yes or No
CK	≥ 5 x ULN or ≥ 3 x ULN with symptoms of rhabdomyolysis ^{d,e}	N/A

BL=baseline; CK=creatinine kinase; DILI=drug-induced liver injury; INR=international normalized ratio; IP=investigational product; N/A=not applicable; TB=total bilirubin

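### SAP 10.3 classifies local-laboratory results for 12 analytes against fixed normal ranges, and the SAP does not say which ULN feeds the ULN-based endpoints

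*SAP*

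**What the plan says.** SAP 10.3 gives fixed ranges for ALP, ALT, AST, GGT, total and direct bilirubin, cholesterol, LDL, HDL, creatinine, creatine and CK. Some vary by sex or age (GGT by sex; CK by sex and, in males, age). None varies by laboratory. The entry for bilirubin, for example, reads "Total Bilirubin 1.71-12.3 umol/L". The rule for the list is: "The abnormal indicators of the selected lab parameters will be derived based on these normal ranges (inclusively".

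The next rule draws the contrast: "For the other lab parameters, the normal ranges and abnormal indicators are based on the values in the data from the central or local labs".

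Protocol 7.4.2 prefers the central laboratory. When a subject cannot attend a scheduled or unscheduled visit, or needs an immediate assessment, it says "the use of a local lab is permissible at the discretion of the Investigator". It continues: "In these cases, the Investigator will obtain the laboratory results and the laboratory normal ranges".

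The shift tables in SAP 10.3 take central or local results. SAP 5.5 admits only scheduled visits to the analyses and sends unscheduled visits to listings.

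SAP 9.1 lists normalization rates and the composite of ALP <1.67 times ULN, total bilirubin at or below ULN and an ALP fall of at least 15%. SAP 10.3 defines Hy's law as ALT or AST at least 3 times ULN with total bilirubin at least 2 times ULN. The visible text does not say which ULN any of these uses, and it does not define normalization.

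**The concern.** Normal limits belong to the laboratory and assay that produced the result. The trial has the local limits obtained, but the SAP uses them only for analytes off the list. The listed analytes are the ones that carry the biochemical efficacy endpoints and the liver and muscle safety summaries. Followed as written, the rule compares a local ALP, ALT, AST, GGT, bilirubin or CK value with limits that may not be those of its own assay.

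The shift tables are directly exposed. The ULN-based efficacy rates and the Hy's law summary are exposed if the programmer takes the ULN from the same list. The SAP leaves that choice open, so it could be made after the data are seen.

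**Working it through.** The plan states no figure to reproduce, so the check is threshold arithmetic.

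**Inputs from SAP 10.3.** ULN for ALP 122 U/L (lower limit 44), for ALT and AST 45, for total bilirubin 12.3 µmol/L. From Protocol 7.2: about 133 subjects. The documents give no local ULNs and no frequency of local testing, so those below are assumptions.

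**Step 1: cut-offs if the fixed ULN is used.**
- ALP: 1.67 × 122 = 203.7 U/L
- ALT or AST for Hy's law: 3 × 45 = 135
- Total bilirubin for Hy's law: 2 × 12.3 = 24.6 µmol/L

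**Step 2: values that change class under an assumed local ALP ULN (U/L).**

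| Local ULN (assumed) | 1.67 × local ULN | Discordant for ≤ULN | Discordant for <1.67 × ULN |
|---|---|---|---|
| 100 | 167.0 | between 100 and 122 | between 167.0 and 203.7 |
| 110 | 183.7 | between 110 and 122 | between 183.7 and 203.7 |
| 122 | 203.7 | none | none |
| 130 | 217.1 | between 122 and 130 | between 203.7 and 217.1 |
| 150 | 250.5 | between 122 and 150 | between 203.7 and 250.5 |

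If the local ULN is below 122, the fixed range is too lenient; if it is above 122, too strict. For ALT and AST, an assumed local ULN of 30 to 60 puts the 3-times limit at 90 to 180, against 135. Total bilirubin follows the same logic and enters both the composite and Hy's law.

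**Step 3: illustrative size per visit.** Subjects changing class = 133 × (share with a local result) × (share of those between the two cut-offs).
- Low end, 2% and 5% assumed: 133 × 0.02 × 0.05 = 0.13 subjects, or 0.1 percentage points
- High end, 10% and 20% assumed: 133 × 0.10 × 0.20 = 2.66 subjects, or 2.0 percentage points

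**Step 4: ALP below the lower limit of 44.** An ALP of 40 U/L is outside 44 to 122 and is flagged. It is also ≤122 and <203.7, and it is below every cut-off in the table, so it meets each ULN-based ALP criterion. It would be miscounted only if normalization were programmed as lying inside both limits. On that reading, with an assumed median of 100 to 117 U/L and log SD of 0.35 to 0.50, the share below 44 is Φ((ln 44 − ln median)/SD):
- Median 117, SD 0.35: Φ(−2.79) = 0.3%
- Median 100, SD 0.50: Φ(−1.64) = 5.0%

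**The case against.** The strongest reply is that this is at most a clarification. The fixed ranges sit in the safety chapter, and nothing in the SAP ties the abnormal indicator to the efficacy endpoints. A criterion of 1.67 times ULN needs a multiple of a limit and cannot be computed from a normal/abnormal flag. The central laboratory is preferred, so local results are the exception. Parts of the efficacy and calculation text are not visible, and a ULN rule could stand there. One common threshold across about 60 sites also has merit. Finally, dividing by a local ULN does not help the ALP reductions of at least 15% and 40% or the changes from baseline, which would still mix raw local and central values.

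Most of this stands as a limit on the point. It does not remove the shift-table problem: the rule in SAP 10.3 is visible and complete, has no exception for local results, and those tables take local results. A common threshold is already supplied by the central laboratory; it does not make another assay's values comparable.

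Three stronger readings are tempting, and the documents do not support them:
- *The best ALP responders are lost from the normalization rate.* The lower limit of 44 supplies the low category that a low-normal-high shift table needs. Protocol 5.1, as literature background, says "optimal survival benefit is realized when normalization of either ALP" is achieved and gives below ULN as the meaning for ALP, with no lower bound.
- *The normalization, composite and Hy's law results are wrong.* The SAP does not state that the fixed ULN feeds them.
- *Urgent results are the most affected.* SAP 5.5 keeps unscheduled visits out of the by-visit analyses, so the exposure is local results at scheduled visits.

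**Conclusion.** The point holds in a limited form. SAP 10.3 can misclassify a local result at a scheduled visit in the shift tables. It can do so in normalization, ALP <1.67 times ULN, bilirubin at or below ULN and Hy's law only if the fixed ULN is used there, which is unstated. Two conditions must both be met: the local ULN differs from the fixed one, and the value lies between the two cut-offs.

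The effect can go in either direction. Its size cannot be derived from the documents. The illustrative 0.1 to 2.7 subjects of 133 per visit (0.1 to 2.0 percentage points) rests wholly on assumed shares, and with matching ULNs it is zero. This is a minor issue, worth settling before any data are summarized because the rule is cheap to state. The undefined term normalization is a separate small gap that the same edit can close.

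**What to change.** In SAP 10.3:
- Apply the fixed ranges to central-laboratory results only.
- Classify local results of the listed analytes, total bilirubin included, against the range recorded with the result.
- Use that same ULN for normalization, 1.67 times ULN, bilirubin at or below ULN and Hy's law, and cross-refer to it from SAP 9.1.
- State that normalization means at or below ULN with no lower bound, and keep the lower limit only for the low category of the shift tables.

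The cost is a few sentences and a small programming rule; the protocol already has sites obtain the local ranges. The downside is that thresholds will differ by laboratory for the few local results. The edit does not resolve the mixing of raw local and central values in change and percent-change endpoints.
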